2.3.3 Background and demographic characteristics

The following demographic and baseline variables will be summarized on the SAF . No listings will be provided.

Demographic variables:

Continuous variables:

- Age (years)
- Height (cm)
- Weight (kg)
- BMI (kg/m^2) will be calculate as (body weight in kilograms) / (height in meters)²
- Volumetric MRI-Whole Brain (cm^3)
- Volumetric MRI-Hippocampus (cm^3)
- Amyloid PET Centiloid

Categorical variables:

- Age group (≤ 64 , 65-69, ≥ 70)
- Sex (Male, Female)
- Years of education: ≤ 12 years, 13-16 years, ≥ 17 years
- BMI (< 25 vs ≥ 25)
- Race (Caucasian, Black, Asian, Native American, Pacific Islander, Other, Unknown)
- Ethnicity (Hispanic or Latino, Other East Asian, Southeast Asian, South Asian, West Asian, Russian, Japanese, Chinese, Mixed Ethnicity, Other, Unknown, Not reported)
- Genotype (HM/ HT)
Note: In database, APOE genotype data is collected from two sources; CRF and vendor (Covance Central Laboratory) load. CRF data is for initial genotyping and vendor load is for genotype confirmation. For deriving genotype for safety analysis, vendor(Covance Central Laboratory) load will be considered. However if the vendor load data is missing the corresponding CRF data will be used
- Amyloid status (Elevated/ Not-Elevated) in HMs
Note: Amyloid status will be Elevated/Not-Elevated as derived by vendor result or derived by the combination of the two results CSF and PET (whichever is Elevated) as described in [Section 2.7.1](#) in subsection Analysis of positive/negative amyloid levels.

Cognitive scales at baseline

Continuous variables:

- MMSE
- RBANS Total score
- Immediate Memory Index
- Delayed Memory Index
- Visuospatial/constructional Index
- Language Index
- Attention Index
- CDR-SOB

Categorical variables:

- CDR Global (Score = 0, Score = 0.5, Score > 0.5)

Other characteristics

The following categorical referral and Alzheimer's disease characteristics will be summarized on the SAF.

- Source of participant's referral (Physician's own practice, Physician referral, Television advertisement, Radio advertisement, Print advertisement, Newsletter/educational material, Advocacy group, ER visit or hospital, Novartis internet site, Non-Novartis internet site, Clinical Trial Registry, Social media, Other)
- Source of the genotyping information (Genematch, 23andMe, Local registry, API015A2201J study, Current study, Other)
- Family history of AD (Father/ Mother, Siblings, Grandparent, Other, None)

Comparability of randomized groups (active versus placebo) at baseline will be assessed via Fisher's exact tests for 2x2 tables or the corresponding Freeman-Halton test for general l x k tables (l, k >= 2) for the selected categorical variables. If Fisher's exact tests are not estimable (e.g. sample size is too large to calculate the statistic) or not adequate, then Chi-squared tests will be performed. Baseline comparability for selected continuous variables will be assessed using t-tests assuming unequal variances in the two groups (active versus placebo). The tests performed together with the p-value will be reported for each baseline variable that has been investigated for comparability. The selected variables for comparisons will be indicated in the TFL shells.

Medical history

Any condition entered as medical history or current medical conditions at baseline will be coded using the MedDRA dictionary effective at the time of the database lock and summarized by system organ class (SOC) and preferred term (PT) on the SAF. No listing will be provided.

2.4 Treatments (study treatment, rescue medication, concomitant therapies, compliance)

2.4.1 Study treatment / compliance

The duration of exposure to study drug is defined as the time (in days) from the first study drug administration to last study drug administration + 31 days.

The duration of exposure will be calculated as

(last dose date + 31 days) – first dose date + 1.

Duration of exposure to CNP520 will be summarized as continuous variable (in days) and categorical variable, using categories ≥ 1 day (any exposure), ≥ 3 months, ≥ 6 months, ≥ 1 year, ≥ 1.5 years.

For each treatment group, the participant-years will be calculated as

(sum of the durations of exposure for all participants in the group)/365.25) and will be summarized.

2.4.2 Prior, concomitant and non-drug therapies

The number and percentage of participants receiving concomitant medications will be summarized on the SAF by ATC class and preferred term (according to the latest World Health Organization drug dictionary (WHO-DD) at the time of database lock, including Anatomical Therapeutic Chemical (ATC) classification code).

The number and percentage of participants receiving significant non-drug therapies will be summarized on the SAF by primary system organ class, preferred term (according to the latest MedDRA dictionary version available at the time of database lock).

2.5 Analysis of the primary objective

Worsening in cognition triggered early termination of the trial and plan is to describe this as rationale for early termination of the trial in CSR before describing the analysis on primary endpoint, hence the below section describes the worsening in cognition and reversibility before the primary endpoint.

2.5.1 Worsening in cognition and reversibility

Worsening in cognition will be assessed based on RBANS, CDR-SOB and APCC for participants in the mSAF.

Tables

The number of participants and the frequency of change (and worsening) in cognition of a specific magnitude (absolute change above specific threshold) will be summarized by visit, including TEC, and EoS as well as last assessment on treatment and last assessment off treatment:

- RBANS decrease (total score and Index scores): ≥ 7 points , and ≥ 14 points from baseline, and from previous visit
- RBANS improvement or increase (total score and Index scores): ≥ 7 points from baseline, and from previous visit
- RBANS no change (change between -6 and 6) from baseline, and from previous visit
- CDR-SOB increase: ≥ 0.5 points, ≥ 1.0 point, and ≥ 1.5 points from baseline, and from previous visit
- CDR-SOB improvement (any decrease) from baseline, and from previous visit
- CDR-SOB no change from baseline, and from previous visit

In addition to the “by visit“ tabulation, the proportion of participants with a clinically relevant worsening from baseline/previous visit will also be shown for

- Either at Week 13 or Week 26 (not at both) – the denominator will be based on participants who have an assessment at both visits;
- Both, at Week 13 and Week 26 – the denominator will be based on participants who have an assessment at both visits;
- At any visit out of Week 13 and Week 26 – the denominator will be based on participants who have an assessment at at least one of the two visits;
- At Any visit up to and including “last on treatment” – the denominator will be based on participants who have an assessment at any post baseline visit (up to and including “last on treatment” assessment).

For the RBANS total score, RBANS index scores and APCC score, effect sizes of change from baseline as well as 80% confidence intervals (CIs) for the effect size will be reported. The effect size (and CI) of change from baseline will be calculated for following post-baseline visits: Week 13 and Week 26, Week 52, TEC, EoS, last assessment on treatment, and last assessment off treatment. The effect size will follow the *Cohen’s d* formula: The raw mean to standard deviation ratio, not model based mean to standard deviation ratio. The effect size will be calculated as the difference between active and placebo in mean change from baseline divided by the pooled standard deviation of the change. Effect sizes and CIs will be calculated (active versus placebo, i.e. the two active CNP520 dose arms will be pooled together without stratification).

Derivation of study specific effect size *d* and corresponding CI

BL = Baseline value; PBL= Post baseline value;

SD = Standard deviation; SE = Standard error; n_1 = Sample size group 1; n_2 sample size group 2; S_1^2 = Variance group 1; S_2^2 = Variance group 2

Numerator: Mean change from BL to PBL active – mean change from BL to PBL control

Denominator: pooled SD defined as

$$SD_{pooled} = \sqrt{\frac{(n_1 - 1)S_1^2 + (n_2 - 1)S_2^2}{n_1 + n_2 - 2}}$$

Where the groups are given by factor treatment (active versus control).

The confidence interval can be derived using the formula proposed by [Hunter and Schmidt 2004](#) and [Nakagawa and Cuthill \(2007\)](#):

$$CI : d \pm z * SE(d)$$

Where z is the 10% Quantile of the normal distribution in case of the 80% CI. The SE(d) is calculated as

$$SE_d = \sqrt{\frac{(n_1 + n_2 - 1)}{(n_1 + n_2 - 3)} \left[\left(\frac{4}{n_1 + n_2} \right) \left(1 + \frac{d^2}{8} \right) \right]}$$

For CDR-SOB, corresponding confidence intervals for the difference between treatment groups will be provided.

Correlation between changes in RBANS total, APCC score and whole brain, hippocampal volume will be reported (correlation coefficient and R square will be reported by treatment group and visit (including also the last assessment on treatment, last assessment off treatment)).

Figures

Graphical presentation (forest plots) of the effect sizes and corresponding confidence intervals for RBANS total, RBANS index scores and APCC score by visit including TEC and EoS, as well as last assessment on treatment and last assessment off treatment.

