9.5.1 Efficacy variables

Clinical Dementia Rating Scale (CDR) sum of boxes (SOB)

A multiplicity adjustment will also be applied to the key secondary variable, as specified in [Section 9.7](#).

The following null hypothesis will be tested for the selected dose within the framework of the multiple testing strategy:

- $H_{03(1)}$: The primary active treatment arm does not differ from matching placebo in the mean change from baseline to month 60 in the CDR-SOB score;

The corresponding alternative hypothesis is:

- $H_{A3(1)}$: The primary active treatment arm differs from matching placebo in the mean change from baseline to month 60 in the CDR-SOB score.

The final secondary analysis of the CDR-SOB score will be performed after all participants reached 60 months of follow-up and will be performed using a longitudinal model for the change from baseline to month 60. It is planned to apply an MMRM adjusted for important factors similar to the approach for the primary analysis model as specified for the APCC. Further specifications will be given in the statistical analysis plan (SAP).

The adjusted least square means (LSMs) for each treatment arm, the difference between the LSMs (active vs placebo), the 2-sided p-values (unadjusted for multiplicity) and associated confidence intervals (CIs) will be calculated from the MMRM analysis and presented for each visit.

Descriptive statistics of the change from baseline in CDR-SOB score will be presented over time.

Sensitivity analysis of the key secondary endpoint will mirror that of the APCC primary efficacy endpoint and described more explicitly in the SAP.

Everyday Cognition scale (ECog) total score

Descriptive statistics of the change from baseline in ECog total score will be presented over time. An analysis of change from baseline will be also performed using longitudinal MMRM model as described for APCC scores in [Section 9.4.2](#).

Tests included in APCC and RBANS

Descriptive statistics of the change from baseline in the individual test scores included in the APCC battery and RBANS, as well as the RBANS Total Scale index score, will be presented over time. An analysis of change from baseline will be also performed using a longitudinal MMRM model as described for APCC score in [Section 9.4.2](#).

[REDACTED]

[REDACTED]

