1.1 Study design

1.1.1 Study Design Summary

The study uses a randomized, double-blind, placebo-controlled, parallel group design with variable treatment duration in cognitively unimpaired participants aged 60 to 75 years, with at least one APOE4 allele (Homozygotes (HMs) or Heterozygotes (HTs)) and if HTs, with evidence of elevated brain amyloid. Overall approximately 2000 participants were planned to be randomized into the study, with a sample size of 800 for the selected dose of CNP520 and placebo, respectively, thereby achieving a 1:1 ratio for the selected CNP520 dose vs placebo. Due to early termination of the study the original planned number of participants will not get enrolled into the study.

The various epochs in the study are specified as follows (see below [Figure 1-1](#)):

Screening Epoch

Treatment Epoch

Follow-up Epoch

Right after signing the Informed Consent (ICF#B), the screening epoch starts. The screening epoch consists of two parts: Screening I and Screening II. In Screening part I, less invasive assessments are performed and genotype is disclosed. Participant may take a few days to reflect on this information before continuing to Screening part II. Screening II includes safety assessments, various cognitive and neuropsychological scales, brain MRI scan, and mandatory amyloid PET scan or a lumbar puncture to verify eligibility of HTs based on brain amyloid status. Amyloid status will subsequently be disclosed. Although HMs are eligible regardless of their brain amyloid status (elevated/not elevated), they will also undergo a PET scan or a lumbar puncture during screening (HMs can opt out of amyloid disclosure). Another reflection period may take place after amyloid disclosure. Altogether, the screening period from signature of ICF#B (part I and part II, including reflection periods when required) is expected to last about 12 weeks.

[figure not shown]
The Treatment Epoch follows a randomized, double-blind, placebo-controlled, parallel group design in which participants receive the investigational treatments or placebo. Participants will be initially randomized to one of the treatment arms in the ratio 2:1:2 (CNP520 50 mg: 15 mg: placebo). The initial regimen is a once daily dose of 50 mg, 15 mg, or placebo throughout

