1.1.3 Randomization and Stratification

All eligible participants will be randomized via Interactive Response Technology (IRT) to one of the treatment arms.

The study will initially be conducted with a randomization ratio of 2:1:2 (CNP520 50 mg: 15 mg: placebo).

The initial regimen is a once daily dose of 50 mg, 15 mg, or placebo throughout the full treatment epoch. If it is determined that the current doses do not provide a suitable benefit/risk profile, a single Lower Dose Regimen (LDR) will be implemented for both active treatment arms through Dose Regimen Modification (DRM) process (see Section 5.1.1 and Section 5.2 of the protocol). This process may be triggered based on DMC recommendation and/or new data for CNP520 or other BACE inhibitors.

In case of DRM, the LDR will consist of a single lower dose regimen selected - either a 50 mg once weekly dose or a 6 mg once daily dose. Both dose regimens are expected to have a similar safety profile. The selection of the dose regimen will be based on both the timing of the DRM decision, as this may restrict options based on availability of supplies, and any further information available at that time, including PK/PD modeling, external data, etc.

The DRM activation will follow the allocation of 2:1:2 across the three treatment arms, resulting in an overall randomization ratio of 3:2 for CNP520 (arm #1 and #2) vs placebo.

The planned total number of randomized participants will not exceed $n = 2000$.

Randomization across treatment arms will be stratified by age group (60 to 64 years, 65 to 75 years), genotype (HM and HT), method used to determine brain amyloid elevation in HT (PET, CSF) and geographic region (North America, Europe, Asia, Other). In case both methods were used, the one indicating elevated amyloid will be captured. If both results indicate elevated amyloid, then the PET method will be used for stratification.

The stratification by age is using age at randomization, not age at screening. Participants who were 75 years old at screening and reached age 76 at randomization due to the long screening time are still eligible and will be randomized into age stratum ≥ 65 .

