2.2 Analysis sets

The following analysis sets will be used.

The **Randomized analysis set (RAS)** will consist of all participants who received a randomization number, regardless of receiving study medication.

The **Safety analysis set (SAF)** will consist of all participants who received study medication.

Note: The above SAF definition is different from the protocol defined SAF definition which restricts to include only those participants in SAF if they have had at least one safety assessment after first dose administration.

The **modified SAF (mSAF)** will consist of all participants of the SAF with at least 3 months exposure duration.

All efficacy analyses (except worsening in cognition and reversibility) and safety analyses will be conducted on the SAF.

In addition, the following sets of participants will be used to understand the composition of analysis sets and disposition of participants.

The **Screened set** will consist of all participants completing any Screening visit. This set should comprise all participants who underwent any screening assessment.

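### The RBANS and APCC effect sizes for the cognitive worsening are unadjusted for baseline score and randomisation factors, which leaves them open to baseline imbalance and gives up a modest amount of precision

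*SAP*

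**What the plan says.** SAP 2.5.1 plans effect sizes with 80% confidence intervals for RBANS total, the RBANS indices and APCC. The visits are Weeks 13, 26 and 52, TEC, EoS, and the last on-treatment and last off-treatment assessments. The estimator is "The raw mean to standard deviation ratio, not model based mean to standard deviation ratio": the active-minus-placebo difference in mean change, "divided by the pooled standard deviation of the change". The active arms are combined: "the two active CNP520 dose arms will be pooled together without stratification". The standard error depends only on the total sample size and d. For the multiplier, the SAP states: "Where z is the 10% Quantile of the normal distribution in case of the 80% CI".

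The analysis set is the mSAF (SAP 2.2 and 2.2.1), which "will consist of all participants of the SAF with at least 3 months exposure duration".

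The protocol planned something different. Protocol 9.4.2 models APCC change with an MMRM containing treatment, visit, baseline score, age group, region and genotype, plus treatment-by-visit and baseline-by-visit terms. For RBANS, Protocol 9.5.1 says: "An analysis of change from baseline will be also performed using a longitudinal MMRM model as described for APCC score in" Section 9.4.2.

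SAP 2.5.4 drops the model-based analyses because there are no Month 60 data and few participants have on-treatment data beyond one year. SAP 2.3.3 tests selected baseline variables between active and placebo but does not use the result to adjust anything.

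**The concern.** SAP 2.5 opens by saying that cognitive worsening led to termination and will be presented first for that reason. For RBANS and APCC, readers will judge the size of the harm and its reversibility from these effect sizes and their forest plots. The Kaplan-Meier intervals in SAP 5.4.1 are given per arm, so they do not fill the gap.

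The absence of Month 60 data explains why the Month 60 contrast is gone. It does not prevent adjustment at the earlier visits, where the SAP already computes d. Protocol 9.8 and SAP Section 3 both state that a longitudinal model adjusting for prognostic factors increases power for APCC.

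Two things are at stake:

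- A change score carries any baseline difference between arms into the estimate. Under the equal-SD model below, a higher active baseline makes worsening look larger and a lower one hides part of it. The mSAF is selected after randomisation, so balance there is not guaranteed.
- Some precision is given up.

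**Working it through.** The SAP states no numerical result for these effect sizes, so there is no figure to reproduce. The check is of how the estimator behaves.

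**Inputs from the documents**

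- Allocation 2:1:2 (SAP 1.1.1), so pooled active to placebo is 3:2.
- SE(d) = √{(N−1)/(N−3) × (4/N) × (1 + d²/8)}, with N = n₁ + n₂ (SAP 2.5.1).
- 80% interval, |z| = 1.2816.

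**Assumptions, not in the documents**

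- Baseline-to-visit correlation r from 0.5 to 0.9.
- Equal baseline and follow-up SDs, relaxed in step 3.
- N = 1000 (600 active, 400 placebo) and d = −0.20.

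**Step 1: effect of a baseline difference.** With unit SDs, the SD of change is √{2(1−r)}. A baseline difference δ shifts mean change by −(1−r)δ, so d shifts in size by δ√{(1−r)/2}. For δ = 0.1:

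| r | shift in d |
|---|---|
| 0.5 | 0.050 |
| 0.7 | 0.039 |
| 0.9 | 0.022 |

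At N = 1000 the chance baseline difference has SD √(1/600 + 1/400) = 0.065. A difference of 0.1 is therefore about 1.5 of its own SDs, which is not remarkable. The SAP half-width is 1.2816 × √{(999/997) × 0.004 × 1.005} = 0.081. At r = 0.7 the shift is 0.039/0.081, or nearly half of that.

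**Step 2: precision with equal SDs.** The variance of change is 2(1−r)s² and the residual variance after baseline adjustment is (1−r²)s². The SE ratio is √{(1+r)/2}: 0.866, 0.922, 0.949 and 0.975 at r = 0.5, 0.7, 0.8 and 0.9. That is 13% to 3% smaller. A simulation of 8000 trials of this size, keeping the raw SD of change as divisor, gave 0.88, 0.92 and 0.97 at r = 0.5, 0.7 and 0.9.

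**Step 3: unequal SDs.** In general the variance saved is (s₁ − r·s₂)², where s₁ is the baseline SD and s₂ the follow-up SD. Take s₂ = 1.2s₁ as an illustration:

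- r = 0.7: variance of change 1 + 1.44 − 1.68 = 0.76; adjusted 1.44 × 0.51 = 0.7344; SE ratio √(0.7344/0.76) = 0.983, a gain of 1.7%.
- r = 0.8: 0.52 against 0.5184, a gain of about 0.2%.

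**Step 4: the SAP's own standard error.** The 4/N term assumes equal groups. At 3:2 the term is N/(n₁n₂) = 4.167/N, so the SAP formula understates the SE by about 2%. Simulated coverage was 78.9% to 79.6% against 80%. With the unequal-allocation formula √{N/(n₁n₂) + d²/(2N)} the half-width is 0.083. Multiplying by the step 2 ratios gives 0.072, 0.077 and 0.081 at r = 0.5, 0.7 and 0.9, against the SAP's 0.081. At r = 0.9 almost nothing is gained over the interval as the SAP would print it.

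**Step 5: choice of divisor.** If the adjusted difference were divided by the residual SD and put through the SAP formula, the full width would stay at 0.163 and |d| would rise to 0.232, 0.218 and 0.205 at the same three values of r. The narrowing appears only with the raw SD of change as divisor and the SE taken from the model.

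**The case against.** The strongest defence is that this is a declared choice. SAP Section 2 makes efficacy reporting descriptive, the report is an abbreviated one, and SAP Section 4 lists the dropped models. No test or decision rests on these intervals, because treatment had already stopped. All of that stands. It makes the point one of robustness and precision, but it does not remove the imbalance problem, since the SAP still publishes between-arm intervals.

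Several stronger readings are tempting and are not supported:

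- **That the intervals are clearly wider than they need be.** The gain rests on an undocumented correlation and on equal SDs, and the SAP's standard error is itself slightly too small at 3:2.
- **That "the two active CNP520 dose arms will be pooled together without stratification" shows the randomisation strata being discarded.** In context it describes combining the two doses. The lack of strata adjustment follows from the formula, not from that phrase.
- **That CDR-SOB is affected in the same way.** SAP 2.5.1 gives no method for its interval. Entry required a global CDR of 0, or 0.5 by exception, so baseline scores probably sit near the floor and the calculation above is unlikely to carry over.
- **That adjustment repairs the mSAF.** It removes a measured baseline difference, not selection on exposure.
- **That adjustment is free of risk.** The SAP's revision history adds APCC to the effect sizes on 21 July 2020, after database lock. Choosing a model at that stage invites a post hoc criticism.

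Two smaller points also stand. RBANS indices are normed on baseline age (SAP 2.7.1), which covers part of one stratification factor; APCC uses raw subtest scores. Baseline imbalance will also be visible from the SAP 2.3.3 summaries, though not corrected.

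**Conclusion.** The point holds as a recommended improvement. The raw d is a legitimate descriptive statistic, computed as stated. Its main weakness is exposure to baseline imbalance in a subset formed after randomisation: about 0.02 to 0.05 in d per 0.1 SD of baseline difference, for r of 0.9 to 0.5 with equal SDs. The precision given up is secondary: an SE about 3% to 13% smaller over the same range, and only 1.7% at r = 0.7 if the follow-up SD is 1.2 times baseline. No figure is given for the further effect of age group, region or genotype, because the documents offer no basis for one.

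**What to change.** Keep the raw d. Add to SAP 2.5.1 a supportive ANCOVA at each visit, or one MMRM across visits, of change on treatment with the protocol covariates: baseline score, age group, region and genotype.

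- **Visits:** RBANS at Weeks 13, 26 and 52; APCC at Weeks 26 and 52 only. APCC needs MMSE items, and SAP Table 5-12 has no Week 13 window for MMSE.
- **Reporting:** the adjusted difference in points with a model-based interval. If it is also standardised, divide by the raw pooled SD of change and take the SE from the model.
- **Labelling:** supportive, and post hoc if added after database lock. Using the protocol's own covariates limits the scope for data-driven choice.
- **Optional:** the same for CDR-SOB, and a term for amyloid method, which the note in Protocol 9.4.2 leaves out of the primary models.

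The cost is a paragraph of SAP text and one model per endpoint. The covariates are baseline scores and randomisation factors that the trial already collects.

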29-May-2020	Prior to DB Lock		
Added a rule to impute missing study treatment end date in section 5.1.1. Updated the censoring rule 3 in section 2.5.5. In section 5.3, added a 30 days window for AEs for liver event criteria (ALT or AST > 3×ULN). In section 5.3, added a 30 days window for injury before the hematuria criteria.
	
01-Jul-2020	Post DB Lock	Creation of addendum 1	
Updated the derivation of Annualized percent change for Volumetric MRI reporting in section 2.5.2 Updated label for “Centiloid” to “Amyloid PET Centiloid” To include MMSE, CDR-SOB and Amyloid PET Centiloid in baseline comparability, the language for baseline comparability paragraph in section 2.3.3 made more generic and flexible
	
12-Jul-2020	Post DB Lock	Creation of addendum 1	
Added the need for analysis of Time to first change in diagnosis classification when participants are
	2.5.4, 2.5.5

				on treatment, Time to first decrease in RBANS Total Score of \geq 14 points when participants are on treatment.	
				Updated wording in definition of last on treatment for clarity in section 2.1.1.	
21-Jul-2020	Post Lock	DB	Creation of addendum 2	Included effect size and CIs for APCC score in section 2.5.1, 2.5.2.	2.5.1, 2.5.2,
				Censoring rule clarified for time to first decrease in RBANS \geq 14 points in section 2.5.5.	2.5.5
				Minor edits in section 4	
23-Jul-2020	Post Lock	DB		A β 1-42/ A β 1-40 ratio added to CSF biomarker reporting in section 2.7.1, 2.7.2.	2.7.1, 2.7.2
29-Jul-2020	Post Lock	DB		Added a note “summaries of distribution of “last on treatment” and “last off treatment” will be presented in CSR Appendix 16.1.9” in section 2. Added section 5.4.2 for additional SAS outputs in Appendix 5 to be used for CSR Appendix 16.1.9	2, 5
30-Jul-2020	Post Lock	DB		Updated section 5.4.2 to include the raw SAS outputs for all the TTE analyses, minor edits.	
				Updated language in section 2 for the note on appendix 16.1.9	
02-Dec-2020	Post Lock	DB	Creation of addendum 3	In section 2.5.1 added additional criteria for change in cognition; improvement (increase) from previous visit by at least 7 points , no change from baseline (change between -6 and 6), no change from previous visit (change between -6 and 6)	2.5.1

11-Jan-2021	Post Lock	DB	Creation of addendum 4	Plasma A β 1-40 summary added to section 2.7.1 under Biomarkers in blood
-------------	-----------	----	------------------------	--

Table of contents

Table of contents	6
List of abbreviations.....	8

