5.4.2 Additional SAS outputs

For the below mentioned analyses, additional (raw) SAS outputs resulted from SAS/STAT procedures or statistical derivations will be presented and used for CSR Appendix 16.1.9:

- Effect Size and 80% Confidence Intervals for APCC score, RBANS Total, RBANS Index scores
- Time to event (TTE) analyses:
 - Time to first confirmed diagnosis of MCI due to AD or Dementia due to AD-SAF
 - Time to first change in diagnosis classification-SAF
 - Time to first change in diagnosis classification when participants are on treatment-SAF

- Time to first change in diagnosis classification when participants are on treatment-mSAF
- Time to first decrease in RBANS Total \geq 14 points when participants are on treatment-SAF
- Baseline comparability

Further details for these additional SAS outputs will be described in the programming notes of the respective shells in the TFL shells Section 16.1.9.

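### The standard error of Cohen's d in SAP 2.5.1 assumes equal groups, but pooled active versus placebo is 3:2, so the 80% intervals are about 2% too narrow

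*SAP*

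**What the plan says.** For three sets of cognitive scores, SAP 2.5.1 plans a standardised difference in change from baseline with an interval: "effect sizes of change from baseline as well as 80% confidence intervals (CIs) for the effect size will be reported". The time points are Weeks 13, 26 and 52, TEC, EoS, and the last assessments on and off treatment. The comparison combines the two doses, with no stratification: "Effect sizes and CIs will be calculated (active versus placebo, i.e. the two active CNP520 dose arms will be pooled together".

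The effect size is the raw difference in mean change divided by a pooled SD, which weights each group's variance by its own n−1. The interval is d ± z × SE(d), with z described as follows: "Where z is the 10% Quantile of the normal distribution in case of the 80% CI". The standard error is

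SE(d) = √{ [(N−1)/(N−3)] × [4/(n1+n2)] × (1 + d²/8) }, where N = n1 + n2.

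SAP 1.1.3 gives 2:1:2 randomisation (50 mg, 15 mg, placebo). For the dose-modification case it spells out the pooled ratio, "resulting in an overall randomization ratio of 3:2 for CNP520 (arm #1 and #2) vs placebo". The same ratio follows from 2:1:2 without a dose modification.

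The results go into tables and forest plots. SAP 5.4.2 also lists them for CSR Appendix 16.1.9: "Effect Size and 80% Confidence Intervals for APCC score, RBANS Total, RBANS Index scores".

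**The concern.** The sampling variance of a two-group standardised difference depends on 1/n1 + 1/n2. The SAP's standard error uses only the total N, through 4/N, which is the equal-group special case. Unequal group sizes therefore enter d, through the pooled SD, but not SE(d). Since 1/n1 + 1/n2 is never below 4/N, imbalance in either direction makes this term too small.

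The output has some prominence. SAP 2.5 says worsening in cognition triggered termination and will be presented in the CSR as its rationale, and the planned inferential and model-based analyses have been dropped. These effect sizes are therefore a main quantification of the cognitive signal and of its reversibility. The stake is limited to whether intervals labelled 80% have that coverage.

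**Working it through.** **Inputs**

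- Confidence level 80%, so |z| = 1.2816 (SAP 2.5.1). The 10% quantile is −1.2816, but the sign is immaterial under ±.
- Active share 3/5 and placebo share 2/5, from 2:1:2 (SAP 1.1.3).
- The documents give no n, SE or interval width for this analysis, so there is no stated figure to reproduce. N and d below are assumptions.

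**Step 1: equal groups.** With n1 = n2 = N/2, 1/n1 + 1/n2 = 2/N + 2/N = 4/N, which is the SAP's term. Simulated coverage of the SAP interval at 250 versus 250 was 79.9% to 80.3%. The formula therefore meets its nominal level at 1:1.

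**Step 2: the planned 3:2 ratio.** 1/(0.6N) + 1/(0.4N) = 1.6667/N + 2.5/N = 4.1667/N.

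- SE as written / correct SE = √(4/4.1667) = √0.96 = 0.9798, which is 2.0% too small.
- Correct width / width as written = 1/0.9798 = 1.0206, which is 2.06% wider.
- Large-sample coverage = 2Φ(1.2816 × 0.9798) − 1 = 0.7908.

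These are values at d = 0. The d² part is unaffected, because (4/N) × d²/8 = d²/(2N) whatever the allocation. The ratio moves only from 0.9798 at d = 0 to 0.9804 at d = 0.5.

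**Step 3: worked example.** Take N = 600 (360 versus 240) and d = −0.2, keeping (N−1)/(N−3) = 599/597 in both versions.

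- As written: √[(599/597) × (4/600) × 1.005] = 0.08199; half-width 1.2816 × 0.08199 = 0.105; interval (−0.305, −0.095).
- Corrected: 600/(360 × 240) + 0.04/1200 = 0.006944 + 0.000033 = 0.006978; √[(599/597) × 0.006978] = 0.08367; half-width 0.107; interval (−0.307, −0.093).

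**Step 4: small samples.** The shortfall in the variance term is 4.1667/4 = 25/24. The factor (N−1)/(N−3) equals 50/48 = 25/24 at N = 51, so at about that size or below it offsets the error fully. Above it the offset is partial.

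**Step 5: simulation.** Normal data, equal variances, 3:2 allocation, 400,000 runs per setting; ranges are over d = 0, −0.2 and −0.3.

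| N | SAP formula | Corrected, factor kept | Corrected, factor dropped |
|---|---|---|---|
| 50 | 79.7–79.9% | 80.6–80.8% | 79.6–79.9% |
| 100 | 79.4–79.6% | 80.3–80.5% | 79.9–80.0% |
| 300 | 79.2–79.3% | 80.1–80.2% | 80.0–80.1% |
| 600 | 79.1–79.2% | 80.0–80.1% | 79.9–80.1% |
| 1000 | 79.0–79.2% | 80.0–80.1% | 79.9–80.0% |

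**Step 6: realised ratio.** The analysis uses the mSAF (at least 3 months' exposure, SAP 2.2), so the ratio at a visit may drift from 3:2. For an active share p the SE ratio is √(4p(1−p)). For an assumed range of 57% to 63%:

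- p = 0.57: 0.9902, SE 1.0% too small, large-sample coverage 79.6%.
- p = 0.63: 0.9656, SE 3.4% too small, large-sample coverage 78.4%.

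**The case against.** The strongest case against raising this concedes the algebra and attacks its consequence and conditions.

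- **It is barely visible.** In the example above both intervals round to (−0.31, −0.09), and the forest plot would look the same. SAP section 2 makes the reporting descriptive. This stands, and it is why the point is minor.
- **Too narrow presumes equal variances.** At 3:2 the SAP's leading term happens to be right if the active variance is about 1.23 times the placebo variance (SD ratio about 1.11). In a simulation at N = 600 and d = −0.2 (300,000 runs, corrected form without the factor), an active SD 1.10 times placebo gave 80.1% coverage as written and 80.9% corrected. At 0.90 times it gave 78.3% and 79.1%. The documents give no SDs, so these are assumptions. The condition is fair and belongs with the magnitude. It does not rescue the formula: Cohen's d on a pooled SD already presumes a common variance, and under that presumption the corrected term is right.
- **Some time points may be sparse.** Few participants have on-treatment data beyond a year, and the December 2019 notification dropped cognitive testing at the modified end-of-study visit. At such points the finite-sample factor shrinks or removes the shortfall. This also stands.
- **The formula is cited, so this is a choice of method.** A citation does not make an equal-group term suit a 3:2 comparison, and SAP 2.5.1 does not present it as an equal-n approximation.

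**Conclusion.** The formula is wrong as written for the comparison it serves. At the planned 3:2 ratio the standard error is 2.0% too small, and the nominal 80% interval covers about 79.1% in large samples. The shortfall falls to about half a percentage point of coverage at N = 100 and essentially disappears near N = 50. These figures assume equal group variances, normal data and a realised ratio close to 3:2.

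The error is minor. It affects the intervals for the RBANS total, RBANS index scores and APCC only; CDR-SOB gets an interval for the group difference, not for d. Nothing in the trial's conclusions turns on it.

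**What to change.** In the SE(d) formula of SAP 2.5.1, replace [4/(n1+n2)] × (1 + d²/8) by

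(n1+n2)/(n1·n2) + d²/(2(n1+n2)),

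using the actual group sizes at each visit. This reduces exactly to the present expression when n1 = n2. The factor (N−1)/(N−3) may be kept or dropped: for N = 50 to 1000, coverage is 80.0–80.8% with it and 79.6–80.1% without it. Then regenerate the effect-size tables, the forest plots and the Appendix 16.1.9 output.

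The cost is one line of the SAP and a rerun of existing programs, with no new data; intervals become about 2% wider. The SAP has already been revised by addendum after database lock for this same output; its change history records "Included effect size and CIs for APCC score in section 2.5.1, 2.5.2". The correction needs no per-dose or model-based effect sizes.
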